10.0 CONCOMITANT MEDICATIONS

To be eligible for enrollment, study participants must require a minimum of three (3) anti-hypertensive medications at the time of entry into the study. Additionally, all subjects will remain on at least three (3) anti-hypertensive medications for the duration of the study.

In addition to the required regimen of hypertensive medications, all study subjects will be required to adhere to a regimen of dual antiplatelet therapy consisting of aspirin (81-325 mg daily) and clopidogrel (75 mg daily), or equivalent medications. If alternative equivalent medications are used, these should be initiated at least three (3) days prior to the implant procedure and continued for at least three (3) months post-procedure. Use of aspirin is required for the duration of study.

Appropriate management of subject's individual risk factors such as statins, smoking cessation, nutrition, diabetes will remain as standard of care and any changes to this regimen will be documented by the study team.

Subjects should be advised of the importance of continuing their medical therapy regimen without consulting with the study center. Subjects should not reduce or stop their anti-hypertensive medication dosage until the 6-month time point, at which time the Principle Investigator may decide to reduce medication as per the site's protocol.

All medications will be recorded on the Concomitant Medication log.

11.0 ADVERSE EVENTS

Safety assessments include adverse events and serious adverse events. The reporting period is from the initial treatment through the last study visit (Month 36).

11.1 DEFINITIONS OF ADVERSE EVENTS

An adverse event is any untoward and unintended sign, symptom or disease temporally associated with the use of an investigational device/drug/biologic or other protocol-imposed intervention, regardless of the suspected cause. Conditions or diseases that are chronic but stable should not be recorded on AE pages of the CRF. Changes in a chronic condition of disease that are consistent with natural disease progression are NOT adverse events and also should not be recorded on the AE pages of the CRF.

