1.0 PROTOCOL SYNOPSIS

TITLE	CALM-FIM_US - C ontrolling and L owering Blood Pressure with the M obiusHD™ - A Prospective Multicenter Safety Study
STUDY OBJECTIVE	To evaluate the safety and performance of the MobiusHD system in subjects with resistant hypertension.
STUDY DESIGN	
This is an open-label, multicenter, first-in-man clinical trial to be conducted inside the United States. Eligible subjects with stage 2 resistant systemic arterial hypertension currently being treated with a minimum of three (3) anti-hypertensive drugs, who consent to study participation will be assigned to treatment with the MobiusHD system.
 
Potential study participants will be consented and then screened at two (2) baseline visits beginning at least 30 days prior to MobiusHD placement. Qualified patients will undergo placement of the MobiusHD under angiographic visualization, and will then be followed for 36 months.
 
Subjects will be enrolled in two (2) phases, as follows:
 
 ▪ Ten subjects will be implanted unilaterally and followed for seven (7) days. ▪ Based on consensus following 7-day clinical outcome analysis by an independent data safety monitoring board (DSMB), 10 additional subjects will be enrolled and implanted bilaterally.
PATIENT POPULATION	Subjects with resistant hypertension receiving at least three (3) anti-hypertensive medications including a diuretic and with no evidence of extracranial carotid disease or significant great vessel/aortic arch atherosclerotic disease.
NUMBER OF PATIENTS	Twenty subjects are to be enrolled at two (2) to ten (10) U.S. clinical sites.
PRIMARY OUTCOME	Safety: Incidence of serious adverse events (SAEs) and unanticipated adverse device effects (UADE) reported for the study population from implantation through six (6) months of follow-up.
SECONDARY OUTCOME	Performance: Decrease in office cuff blood pressure (BP).
ADDITIONAL OUTCOMES	
Change in heart rate
 
Reduction of medication post 6-month follow-up
 
365-Day safety and efficacy
 
Long term safety and efficacy – one (1) to three (3) years

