18. Moderate to severe reactive airway disease, chronic obstructive pulmonary disease, or primary pulmonary hypertension;
19. Uncompensated congestive heart failure or known severe reduction in left ventricular function (EF < 30%);
20. Uncontrolled co-morbid medical condition that would adversely affect participation in the trial;
21. Non-controlled diabetes mellitus;
22. Active infection within the last month;
23. Co-morbid condition that reduces life expectancy to less than one (1) year;
24. Mental health issues that would prohibit the subject's ability to meet the protocol requirements;
25. Currently taking an imidazoline receptor agonist or receiving central sympathetic treatment;
26. Enrolled in a concurrent clinical trial;
27. Unable or unwilling to fulfill the protocol follow-up requirements;
28. Subject is a prisoner or member of other protected population;
29. Planned surgery or other procedure within the next six (6) months; or
30. Deep venous thrombosis (DVT) within the last year or documented recurrent DVT.

Baseline Screening Visit 2 – (Day 15 – 30) - Assessed on Day 30

1. ICA lumen diameters < 5 mm or > 11.75 mm within the planned location of the device placement via CTA or MRA;
2. Carotid hypersensitivity detected by carotid massage or typical history, as described in the study protocol; and
3. Significant aortoiliac or common femoral artery disease that will prohibit safe femoral access.

Day of Procedure – Angiographic

1. Evidence of plaque, ulceration or any stenosis by angiographic evaluation in orthogonal views of the carotid artery. Lumen diameters will be assessed to exclude subjects with ICA lumen diameters smaller than 5 mm or larger than 11.75 mm within the planned location of the device placement;
2. Any plaque or ulceration on the arch angiogram involving the aortic arch and/or the origin of the great vessels;
3. Inappropriate anatomy of the carotid bifurcation for deployment of the MobiusHD, including, but not limited to, tortuosity of the extracranial vessels and significant angulation of the common carotid artery bifurcation; and

4. Type III arch or horizontal takeoff of the left carotid from the innominate and calcification of the carotid bulb.

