8.2 STUDY ENROLLMENT

The number of subjects to be enrolled in the study is up to 20. This sample size is estimated to be sufficient to yield acceptable, first-in-man, safety and effectiveness data for initial analysis and to support future regulatory submissions. It is anticipated that up to ten (10) centers inside the United States will be needed to enroll this study in a timely fashion. Each investigational site will be expected to enroll at least two (2) and up to eight (8) subjects.

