11.1.1 Serious Adverse Events (SAE)

An AE should be classified as an SAE and reported as such, if it meets one or more of the following criteria:

- It results in death (i.e., the AE actually causes or leads to death)
- It is life threatening (i.e., the AE places the subject at immediate risk of death)
- It requires or prolongs inpatient hospitalization
- It results in persistent or significant disability/incapacity (i.e., the AE results in substantial disruption of the subject's ability to conduct normal life functions)
- It results in a congenital anomaly/birth defect in a neonate/infant born to a mother exposed to the investigational product
- It is considered a significant medical event by the investigator based on medical judgment (e.g., may jeopardize the subject or may require medical/surgical intervention to prevent one of the outcomes listed above).

If a subject is hospitalized to undergo a medical or surgical procedure as a result of an AE, the event responsible for the procedure, not the procedure itself, should be recorded as the event. For example, if a subject is hospitalized to undergo coronary bypass surgery, record the heart condition that necessitated the bypass.

Hospitalizations for the following reasons will not be recorded as SAEs:

- Hospitalization or prolonged hospitalization for diagnostic or elective surgical procedures for preexisting conditions
- Hospitalization or prolonged hospitalization required to allow outcome measurement for the study
- Hospitalization or prolonged hospitalization for scheduled therapy of the target disease of the study.

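### The natural-progression exclusion in Section 11.1 has no exception for serious events, so a non-fatal serious worsening of a chronic condition can be left out of the primary SAE incidence

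*Combined protocol and SAP*

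**What the plan says.** The primary outcome in the synopsis (Section 1.0) is "Incidence of serious adverse events (SAEs) and unanticipated adverse device effects (UADE) reported for the study population", counted from implantation to six months.

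Section 11.1 defines an adverse event broadly, without regard to cause, and then removes two groups: chronic conditions that stay stable, and a second group described as follows: "Changes in a chronic condition of disease that are consistent with natural disease progression are NOT adverse events". Changes in the second group are also kept off the AE pages of the CRF. The section does not define natural progression, say who decides, or treat serious changes differently.

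Section 11.1.1 opens with "An AE should be classified as an SAE and reported as such" and then lists the seriousness criteria, including inpatient hospitalisation. It exempts three kinds of admission. Two matter here: "Hospitalization or prolonged hospitalization for diagnostic or elective surgical procedures for preexisting conditions" and "Hospitalization or prolonged hospitalization for scheduled therapy of the target disease of the study". The third is admission needed to measure study outcomes.

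Sections 11.5 and 16.1 have the DSMB adjudicate SAEs and UADEs and judge whether SAEs relate to the device or procedure. Section 11.0 runs AE reporting to Month 36 under the same definitions.

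**The concern.** The exclusion acts before anyone asks whether the event is serious. Followed as written, it lets a site treat a serious, non-fatal deterioration of a chronic illness as no adverse event at all. That event then has no route to becoming an SAE.

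This is an open-label trial with no control arm, and its primary result is a descriptive safety rate. Whether a deterioration reflects underlying disease is a question of attribution. The protocol already has a place for that question: the relatedness assessment in Section 11.2.3, followed by DSMB evaluation. Section 11.1 allows it to be settled earlier, where the event disappears from the count instead of being counted and called unrelated. At stake are the accuracy of the six-month rate, its consistency across sites, and the one-to-three-year safety outcome that uses the same definition.

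**Working it through.** The plan gives no event rate, power calculation or SAE limit, so there is no figure to reproduce. The check is a reading of the text, with arithmetic for scale.

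**Path of an event through the text**

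1. A subject enrols with a permitted chronic condition. Section 6.2 excludes heart failure only when it is uncompensated or the ejection fraction is known to be below 30%. For diabetes it excludes only "Non-controlled diabetes mellitus". Compensated heart failure and controlled diabetes can therefore enter.
2. The subject has an unscheduled admission for worsening of that condition. This meets the hospitalisation criterion in 11.1.1. It is not a diagnostic or elective surgical admission, not for outcome measurement, and not scheduled treatment of hypertension, so no 11.1.1 exemption applies.
3. If the site judges the change to be natural progression, 11.1 says it is not an AE. Section 11.1.1 then has no AE to classify, and the event reaches neither the primary SAE count nor SAE adjudication under 11.5 and 16.1. The sponsor's trend review in 16.1 covers AEs, so the event misses that too.

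**Text in tension with the exclusion**

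- The opening of 11.1, and Section 11.2, make cause irrelevant to whether an AE is recorded.
- The bypass-surgery example in 11.1.1 has the underlying heart condition recorded. It applies to an admission resulting from an AE, so it presupposes the answer.
- The hospitalisation exemptions in 11.1.1 are narrow, which suggests that other admissions were meant to count.
- Section 11.3 lists chronic and recurrent hypertension and renal insufficiency as anticipated adverse events. Heart failure and diabetes are not on the list.
- Section 11.2 uses congestive heart failure as a sample event term but does not say whether worsening of pre-existing failure qualifies.

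**Scale**

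Inputs: up to 20 subjects (Section 8.2), planned as two cohorts of 10 (Section 5.0). Section 13.0 summarises AEs as numbers and percentages of patients, so I count subjects.

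- Change per omitted subject with no other SAE: 1/20 = 5 points; 1/10 = 10 points. For two such subjects: 2/20 = 10 points; 2/10 = 20 points.
- Exact (Clopper-Pearson) 95% limits for x of n are the 2.5% quantile of Beta(x, n−x+1), or 0 when x = 0, and the 97.5% quantile of Beta(x+1, n−x). The plan does not ask for intervals; these are for scale.

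| True count (assumed) | Incidence (95% CI) | Reported if omitted (95% CI) |
|---|---|---|
| 1/20 | 5% (0.1 to 24.9) | 0/20, 0% (0 to 16.8) |
| 1/10 | 10% (0.3 to 44.5) | 0/10, 0% (0 to 30.8) |

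- The chance that at least one subject has such an event is 1 − (1 − p)^n, where p is an assumed six-month probability per subject. For p = 2%, 5%, 10% and 20% it is 33%, 64%, 88% and 99% with n = 20, and 18%, 40%, 65% and 89% with n = 10. The documents support no particular p, and these are chances that an event occurs, not that a site would exclude it.

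**The case against.** The strongest reply is that the text permits this omission but does not require it. Subjects enter only while their heart failure is compensated or their diabetes controlled, so an acute decompensation can be read as a new untoward event, to be recorded whatever its cause. That stands, and it is why the point says such an event can be omitted, not that it will be.

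Several safeguards also count:

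- Section 9.0 requires an SAE form for every death, so fatal events are covered.
- Section 11.1.2 defines a UADE without using the AE definition, though the effect must be device-associated and not previously identified.
- Section 16.5 has monitors look for omitted AEs in clinical records, though they would apply the same definition.
- Section 8.18 sends tests from unscheduled visits to the sponsor for DSMB adjudication.
- Sections 1.0 and 5.0 give the DSMB seven-day and available data, and the FDA an interim report if bilateral treatment is sought.
- Section 13.0 promises a full profile and narrative for each subject.

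These reduce the consequence. None turns an excluded event into a counted SAE.

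A reader might infer three stronger points that the documents do not support.

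- *That 11.1.1 and 11.3 contradict 11.1.* The exemptions in 11.1.1 operate on something that is already an AE. Section 11.3 lists anticipated events without saying that each must be reported when judged natural progression, and recurrent hypertension may mean loss of a device effect. This is tension, not contradiction.
- *That the reported rate is materially biased.* The frequency of such events is unknown, and the entry exclusions plausibly make them less common.
- *That enrolment concentration measures the bias.* Section 8.2 says "Each investigational site will be expected to enroll at least two (2) and up to eight (8) subjects", so one site may hold 2/20 = 10% to 8/20 = 40% of subjects. That is the share subject to one site's reading of 11.1, not an effect on the SAE rate.

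**Conclusion.** The point holds in limited form. The stated rule can remove a non-fatal serious worsening of a chronic condition from the primary SAE incidence and from DSMB SAE adjudication. The error can run only downwards: 5 points of 20, or 10 points of a 10-subject cohort, for each affected subject with no other SAE.

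This assumes that a site applies 11.1 to such an event. That the investigator makes the call is itself inferred, from the relatedness assessment in 11.2.3 and the sign-off of AE forms in 16.2. The sample CRFs (Appendix III) appear only as a title in the copy reviewed, so any completion instructions there could not be checked.

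No pass/fail decision is at risk: Section 13.0 plans no formal test, and the suspension provision in Section 22.0 gives no number. The issue is the accuracy and consistency of a descriptive rate that is the trial's main result. I hold this with moderate confidence and regard it as a cheap improvement.

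**What to change.** Add one sentence to Section 11.1: the natural-progression exemption does not apply to any event meeting a seriousness criterion in 11.1.1, subject to the hospitalisation exceptions already listed there; such events are recorded as SAEs and adjudicated by the DSMB, and attribution to underlying disease is handled as relatedness under 11.2.3.

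The cost is a sentence of protocol text, a few more SAEs to adjudicate, and possibly a less favourable SAE rate.

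I would not go further and require every worsening of an 11.3-listed condition to be recorded. Hypertension is on that list and subjects enter with office systolic pressure of at least 160 mmHg, so blood-pressure rises would become AEs with no threshold and would partly duplicate the blood-pressure outcome.

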11.1.1 Serious Adverse Events (SAE)

An AE should be classified as an SAE and reported as such, if it meets one or more of the following criteria:

- It results in death (i.e., the AE actually causes or leads to death)
- It is life threatening (i.e., the AE places the subject at immediate risk of death)
- It requires or prolongs inpatient hospitalization
- It results in persistent or significant disability/incapacity (i.e., the AE results in substantial disruption of the subject's ability to conduct normal life functions)
- It results in a congenital anomaly/birth defect in a neonate/infant born to a mother exposed to the investigational product
- It is considered a significant medical event by the investigator based on medical judgment (e.g., may jeopardize the subject or may require medical/surgical intervention to prevent one of the outcomes listed above).

If a subject is hospitalized to undergo a medical or surgical procedure as a result of an AE, the event responsible for the procedure, not the procedure itself, should be recorded as the event. For example, if a subject is hospitalized to undergo coronary bypass surgery, record the heart condition that necessitated the bypass.

Hospitalizations for the following reasons will not be recorded as SAEs:

- Hospitalization or prolonged hospitalization for diagnostic or elective surgical procedures for preexisting conditions
- Hospitalization or prolonged hospitalization required to allow outcome measurement for the study
- Hospitalization or prolonged hospitalization for scheduled therapy of the target disease of the study.

11.1.2 Unanticipated Adverse Device Effects (UADE) (where applicable)

An unanticipated adverse device effect (UADE) is any serious adverse effect on health or safety or any life-threatening problem or death caused by or associated with a device, if that effect, problem, or death was not previously identified in nature, severity or degree of incidence. Anticipated adverse events are identified in Section 11.3.

11.2 ADVERSE EVENT ASSESSMENT AND DOCUMENTATION

All subjects who have been exposed to the study treatment will be evaluated for adverse events. All adverse events, regardless of severity and whether or not they are ascribed to the study treatment, will be recorded in the source documents and CRF using standard medical terminology.

All adverse events will be evaluated beginning with onset, and evaluation will continue until resolution is noted, or until the investigator determines that the subject's condition is stable. The investigator will take appropriate and necessary therapeutic measures required for resolution of the adverse event. Any medication necessary for the treatment of an adverse event must be recorded on the concomitant medication case report form.

All AEs will be characterized by the following criteria:

- Event term
- Intensity or severity
- Expectedness
- Relationship to study treatment
- Outcome
- Treatment or action taken.

Whenever possible, recognized medical terms should be used when recording AEs. Colloquialisms and/or abbreviations should not be used. Only one medical concept, preferably a diagnosis instead of individual symptoms, should be recorded as the event.

If more than one distinct adverse event occurs, each event should be recorded separately. However, if known at the time of reporting, a diagnosis (i.e., disease or syndrome) should be recorded on the CRF rather than individual signs and symptoms (e.g., record congestive heart failure rather than dyspnea, rales, and cyanosis). However, if a constellation of signs and/or symptoms cannot be medically characterized as a single diagnosis or syndrome at the time of reporting, each individual event should be recorded as a separate AE. A diagnosis that is subsequently established should be reported as follow-up information. However, signs and symptoms that are considered unrelated to an encountered syndrome or disease should be recorded as individual AEs (e.g., if congestive heart failure and severe headache are observed at the same time, each event should be recorded as an individual AE).

Adverse events occurring secondary to other events (e.g., sequelae) should be identified by the primary cause; a "primary" event, if clearly identifiable, should represent the most accurate clinical term to record as the AE event term. For example:

Orthostatic hypotension ⇒fainting and fall to floor ⇒head trauma ⇒neck pain

The primary event is orthostatic hypotension and the sequelae are head trauma and neck pain.

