13.0 STATISTICAL METHODS

Since this is a pilot study designed to evaluate the initial safety of the MobiusHD in subjects with stage 2 hypertension, no formal hypothesis testing is planned. Complete data for each study subject will be presented in an individual patient profile consisting of all CRF fields and a narrative summary. Additionally, where appropriate, descriptive statistics will be used to tabulate and summarize study outcomes. Background and demographic characteristics will be presented. Continuous variables will be summarized by descriptive statistics (sample size, mean and standard deviation, median, minimum and maximum). Discrete variables will be summarized by frequencies and percentages. Adverse events will be summarized by presenting the number and percentage of patients having any adverse event. Any other information collected (such as severity or relationship to study device) will be listed as appropriate. Any statistical tests performed to explore the data will be used only to highlight any interesting comparisons that may warrant further consideration.

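### Section 11.2 files a secondary event under its primary cause with no exception for a serious sequela, so event-level and type-specific SAE counts can be understated

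*Combined protocol and SAP*

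**What the plan says.** The primary outcome in the Synopsis is "Safety: Incidence of serious adverse events (SAEs) and unanticipated adverse device effects (UADE) reported for the study population", from implantation through six months. It does not say whether subjects or events are counted.

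Section 11.2 governs what is entered as an event. It contains two instructions:

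- General: "If more than one distinct adverse event occurs, each event should be recorded separately".
- For secondary events: "Adverse events occurring secondary to other events (e.g., sequelae) should be identified by the primary cause". Where the primary event is clearly identifiable, it "should represent the most accurate clinical term to record as the AE event term".

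The example that follows runs from orthostatic hypotension, through a faint and fall, to head trauma and neck pain. It concludes: "The primary event is orthostatic hypotension and the sequelae are head trauma and neck pain".

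The same section has each AE characterized by its term, severity, expectedness, relationship, outcome and action taken. Section 11.1.2 makes UADE status depend on whether the effect is new: "if that effect, problem, or death was not previously identified in nature, severity or degree of incidence". It refers to Section 11.3 for the anticipated events. Section 13.0 plans this summary: "Adverse events will be summarized by presenting the number and percentage of patients having any adverse event". It specifies no table of SAEs by type.

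**The concern.** The secondary-event rule is an instruction to sites, and its own example applies it to an injury, which is a distinct diagnosis and not a symptom of low blood pressure. Nothing limits the rule to non-serious sequelae. The general instruction on distinct events points the other way, but the section does not say which one governs when a distinct diagnosis follows from another event. Two sites could code the same case differently and both claim to follow the protocol.

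This matters because the attributes that feed the primary outcome are assigned to each recorded AE. A sequela without its own record has no term, expectedness or relationship of its own. Several events on the Section 11.3 list can stand in a causal chain, for example hypotension, dissection or vessel thrombosis followed by stroke. What is at stake is whether a tally built on event terms shows the harm that occurred, and whether an unlisted serious sequela is separately considered as a possible UADE.

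**Working it through.** **Inputs.** Cohort size 10 and total 20 (Synopsis; Section 5.0). The documents give no event rate, power calculation or confidence level for this point, and Section 13.0 plans no formal hypothesis test. There is therefore no planned figure to reproduce. The case below is an assumption, used only to trace what the rule does.

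**Step 1: which counts move?** Suppose one subject has a dissection that leads to a stroke with hospitalization.

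Section 11.1.1 decides seriousness by consequences, such as hospitalization or the disability criterion, "It results in persistent or significant disability/incapacity". The dissection, having led to hospitalization, is then itself an SAE.

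| Count | Stroke filed under dissection | Stroke recorded separately |
|---|---|---|
| Subjects with any AE | 1 | 1 |
| Subjects with any SAE | 1 | 1 |
| SAE events (if both are serious) | 1 | 2 |
| Strokes, cohort of 10 | 0/10 = 0% | 1/10 = 10% |
| Strokes, all 20 | 0/20 = 0% | 1/20 = 5% |

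The subject-level counts are the same under either rule. The event count and the type-specific count are not.

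**Step 2: precision around the type-specific count.** Exact (Clopper-Pearson) 95% limits:

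- x = 0: lower limit 0, upper limit 1 − 0.025^(1/n). For n = 10 this is 30.9%; for n = 20 it is 16.8%.
- x = 1: lower limit 1 − 0.975^(1/n), upper limit the 97.5th percentile of Beta(2, n − 1). For n = 10 this gives 0.3% to 44.5%; for n = 20, 0.1% to 24.9%.

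The intervals overlap heavily, as they must with so few subjects. What changes is the qualitative statement: no stroke observed, or one.

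**Step 3: the UADE route.** Take the protocol's own example and assume that the head trauma is serious.

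1. The recorded term is orthostatic hypotension.
2. Hypotension is on the Section 11.3 list; head trauma is not.
3. Expectedness is one of the attributes assigned to each recorded AE, so with one record there is one expectedness judgment, attached to hypotension.
4. Section 11.1.2 also looks at severity and incidence, so the investigator could still call this hypotension unanticipated in severity. The text permits that but does not prompt it, and the head trauma gets no entry of its own.

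For stroke the route is different. Stroke is on the Section 11.3 list, so a separate record would not make it unanticipated in nature. The UADE concern therefore applies mainly to unlisted sequelae.

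**The case against.** The best case against is that the text does not require a stroke to go unrecorded and that other provisions would bring it to light.

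- Section 11.2 also asks for all AEs to be recorded, prefers a diagnosis as the event term, and separates distinct events. Stroke is defined in its own right and listed in Section 11.3. The example does not call the head trauma serious and does not mention stroke.
- The only AE summary that Section 13.0 specifies is at subject level, and it does not move. No stroke rate is a planned endpoint.
- The outcome categories in Section 11.2.4 ask for sequelae to be specified when an event resolves with them. Under Section 11.5 the DSMB, which includes a neurologist, adjudicates every SAE and UADE from event summaries and imaging. Section 13.0 gives each subject a full profile and narrative. Section 5.0 has all available clinical data go to FDA with any request for bilateral treatment.

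Much of this stands, and it rules out three stronger readings that a reader might infer. The first is that a serious sequela is never recorded as its own event: with two unreconciled instructions, non-recording is possible but not certain. The second is that the subject disappears from the safety counts: the consequence makes the primary event serious, so the subject remains. The third is that the DSMB and FDA would see only a mild term such as hypotension: the adjudication material and narratives make that unlikely in 20 individually reported subjects.

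These safeguards do not fill the remaining gap. The request to specify sequelae is attached to one outcome category only, not to ongoing events or deaths. The sections on the DSMB give no rule for splitting or recoding a combined event. A narrative does not correct a table built from event terms.

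**Conclusion.** The point holds in a limited form. Section 11.2 gives a rule that, followed as written and as illustrated, can place a serious and distinct sequela under another event's term, and the section does not say when the opposing instruction takes over. The effect is confined to counts of SAE events, counts of particular SAE types, and the separate expectedness assessment of sequelae absent from Section 11.3.

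In size, one affected case lowers a type-specific rate by 10 percentage points in a cohort of 10 or 5 points in 20, and lowers the SAE event count by one. These figures assume a single such case and are not a forecast. The finding that subject-level counts do not change assumes that investigators judge the primary event's seriousness by what it led to. The understated SAE event count bears on the primary outcome only if its incidence is read as events, which the Synopsis leaves open.

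This should be corrected, but it does not invalidate the planned descriptive analysis.

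**What to change.** 1. In Section 11.2, restrict the primary-cause rule to secondary signs and symptoms that are not serious.
2. Add a sentence to this effect: any sequela that itself meets a criterion in Section 11.1.1, or is a stroke or TIA, is entered as a separate AE with its own term, seriousness, expectedness and relatedness, and is linked to the primary event.
3. Amend the worked example so that head trauma, if serious, appears as its own linked SAE.
4. In Section 13.0, add a table of SAEs by type.

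The cost is a few sentences and one table. The reported number of events will rise slightly, and the link lets a reader see which events belong to one chain. The AE form needs a linking field if it does not already have one; the sample case report forms (Appendix III) are not shown, so this could not be checked. No treatment or assessment changes.
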